
OBJECTIVES	ENDPOINTS	JUSTIFICATION FOR ENDPOINTS

3) Class (new arrivals [VP and 1st semester] vs. 5th semester)
 
 Subset analyses of Primary Endpoint and Secondary Endpoints 1-7 in the subset of participants excluding those participants categorized as immunosuppressed (reporting use of immunosuppressive medications or treatments or occurrence of immunosuppressive medical conditions in baseline questionnaire) 		

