8 SAMPLE SIZE

The estimated number of participants needed to achieve the study's primary objective is 430 (215 in each group). The sample size was calculated using the approach for comparing two negative binomial rates based on true rates (Approach 2 in [17]), implemented using the function *power.nb.test* in package 'MKmisc' in R, and assuming the following parameter values:

- Alpha level = 0.05
- Targeted power = 0.8
- Event rate for control group = 2 (expected mean number of new CID episodes [composite primary endpoint] over 26 weeks)
- Rate ratio under alternative hypothesis = 0.75
- Average length of participation (accounting for drop-out and non-response) = 21 weeks (0.8 of 26-week observation period)
- Negative binomial dispersion parameter (k in [17]) = 0.4

The three nuisance parameters (average length of participation, event rate for control group and negative binomial dispersion parameter) were estimated from data collected over 7 weeks of a pilot study of rates of CID episodes in 90 RUSVM students (40 in 1st semester and 50 in 5th semester) from 21 May to 8 July, 2018 (weeks 3 through 9 of summer semester).

An internal pilot study will be done using data from the first 300 participants to complete the study. As the expected enrollment rate is <100 participants per semester, this will allow capture of seasonal variation in event rates (≥ 3 semesters in internal pilot study). The three nuisance parameters will be re-estimated from the internal pilot study data and the sample size recalculated, using a blinded sample size re-estimation method for count data [18, 19], which maintains required power without an increase in the type I error. The sample size will only be increased and not decreased on the basis of the internal pilot study (that is, if the recalculated sample size is smaller than the original sample size, the original sample size will still be used).

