11 ALLOCATION

11.1 SEQUENCE GENERATION

Allocation of participants to study arms will be done by restricted randomization (permuted block design with stratification). Stratification will be by cohort (three cohorts per year: January, May and September) and sex (within cohort). Within strata, randomization will be done by computer-generated randomly permuted blocks of varying size (using the function *blockrand* in the package 'blockrand' in R). Enrolled students will be allocated in a 1:1 ratio to one of the two study arms.

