14 STATISTICAL METHODS

The analysis of the primary endpoint and secondary endpoints 1-7 will be conducted after all randomized participants have completed the study (one week after receipt of the final weekly survey) or have withdrawn from the study, whichever occurs first. Primary analysis will be based on intention-to-treat analysis of all events (that is, not just occurrence of first events). The comparison of incidence rates of CID episodes (primary endpoint and secondary endpoints 1-7) between the treatment arms will be performed using a negative binomial regression model, which accounts for different lengths of observation period. Participants' number of CID episodes will be modelled as a function of treatment group, with the number of weeks of observation included as an offset in the model. This analytic model estimates the rate ratio, λ_t / λ_c , which quantifies the risk of CID episodes associated with rabies vaccination (λ_t) in comparison to placebo injection (λ_c). Statistical significance will be controlled at the 2-sided, 0.05 alpha level, and the estimated rate ratio compared with 1, assuming the following statistical hypothesis:

H_0 (null hypothesis): Rate ratio = 1

H_1 (alternative hypothesis) Rate ratio $\neq 1$

Treatment effect will be based on the coefficient in the model. Statistical significance at the pre-specified alpha level will be based on a Wald testing procedure. CID rates (primary

endpoint and secondary endpoints 1-7) for rabies vaccine and placebo, and the rate ratio, will be presented and will include 95% confidence intervals.

A detailed description of the statistical methods that will be used for the primary and secondary endpoints will be provided in a Statistical Analysis Plan (SAP).

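### The primary model adjusts for no baseline factor; pre-specifying class, cohort and sex could recover some precision (for class, 0 to about 4 points of power) at little cost

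*Combined protocol and SAP*

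**What the plan says.** - **Model (Section 14).** The participant's "number of CID episodes will be modelled as a function of treatment group" in a negative binomial regression with an offset for weeks observed. No covariate is named. A Wald test is used, and "Statistical significance will be controlled at the 2-sided, 0.05 alpha level". Fuller detail is deferred to a SAP, and no such SAP text is in the document reviewed.
- **Randomization (Section 11.1).** "Stratification will be by cohort (three cohorts per year: January, May and September) and sex (within cohort"). Section 11.2 numbers the envelopes from 1 for each sex in each cohort. Class plays no part.
- **Class.** Section 5.2.1 makes being in VP, 1st or 5th semester the inclusion criterion, so class is known before allocation. Section 5.1 enrols all three groups every semester, so each cohort mixes classes. Section 3.2.2 lists class ("new arrivals [VP and 1st semester] vs. 5th semester") with sex and season as subgroup factors that might modify the vaccine effect.
- **Sample size (Section 8).** 430 participants, 215 per arm, from "Targeted power = 0.8", "Event rate for control group = 2", "Rate ratio under alternative hypothesis = 0.75", follow-up of 0.8 of the 26 weeks and k = 0.4. The nuisance values came from a pilot in "90 RUSVM students (40 in 1st semester and 50 in 5th semester"). A blinded re-estimation may raise the sample size but not lower it.

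**The concern.** Of the three subgroup factors, sex and season (through cohort) are balanced by the stratified blocks. Class alone is left to chance in the design and then also left out of the analysis. If newly arrived and settled students fall ill at different rates, that difference remains in the dispersion as unexplained variation, and an uneven class split between arms goes uncorrected. Leaving out cohort and sex means that the analysis also does not use the factors on which allocation was balanced. What is at stake is the precision of the primary rate ratio, when the data that would improve it are already collected.

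**Working it through.** **Inputs from the documents:** two-sided alpha 0.05, power 0.80, control rate 2, rate ratio 0.75 (vaccine rate 1.5), exposure 0.8, k = 0.4 (Sections 8 and 14).

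**Assumptions, not in the documents:** k = 0.4 is an overall value across classes; half of participants are in each class; the ratio r of illness rates between classes lies between 1.0 and 2.0; the vaccine effect is the same in both classes.

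**1. Reproduce the plan's figure.**
V = (1/0.8)(1/2 + 1/1.5) + 2 × 0.4 = 1.458 + 0.800 = 2.258.
n per arm = (1.960 + 0.842)² × 2.258 / (ln 0.75)² = 214.2, so 215 per arm and 430 in total, as stated.
Power at 215 per arm = Φ(0.2877 × √(215/2.258) − 1.96) = 80.2%. The SE of the log rate ratio is √(2.258/215) = 0.102.

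**2. Remove the between-class part of k.** With equal classes, CV² = ((r − 1)/(r + 1))², and within-class k = 1.4/(1 + CV²) − 1.

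**3. Power with class in the model.** Keep the mean control rate at 2, so the class control rates are 4/(1 + r) and 4r/(1 + r). For a class with control rate λ, V(λ) = (1/0.8)(1/λ + 1/(0.75λ)) + 2k = 2.917/λ + 2k. The information is half of 1/V from each class, and the combined V is its inverse.

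| r | class control rates | within-class k | combined V | power | gain (points) |
|---|---|---|---|---|---|
| 1.0 | 2.00, 2.00 | 0.400 | 2.258 | 80.2% | 0 |
| 1.1 | 1.90, 2.10 | 0.397 | 2.253 | 80.2% | 0.1 |
| 1.25 | 1.78, 2.22 | 0.383 | 2.230 | 80.6% | 0.5 |
| 1.5 | 1.60, 2.40 | 0.346 | 2.170 | 81.7% | 1.5 |
| 2.0 | 1.33, 2.67 | 0.260 | 2.022 | 84.3% | 4.1 |

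Letting new arrivals be 30% to 67% of participants, with either class having the higher rate, gives gains of 0.4 to 0.5 points at r = 1.25 and 2.7 to 4.7 at r = 2. A simulation of 1,500 trials per case moved power from 80.5% to 82.3% at r = 1.5 and from 80.5% to 83.4% at r = 2, with Monte Carlo error of about 1 point per estimate.

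**4. Chance imbalance.** The SD of the arm difference in class share is √(2 × 0.25/215) = 0.048. A one-SD imbalance shifts the log rate ratio by about 0.048 × (r − 1)/((r + 1)/2), which is 0.011, 0.019 and 0.032 at r = 1.25, 1.5 and 2. Against an SE of 0.102, that is about 10% to 31% of one SE.

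**5. If 0.4 were a within-class k.** Section 8 does not say which it is. The overall k would then be larger. At r = 1.25, 1.5 and 2, unadjusted power would be 79.6%, 78.2% and 74.9%, against 80.0%, 79.8% and 79.1% with class in the model.

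No size is given for cohort or sex, because the documents contain no illness rates by either.

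**The case against.** The strongest reply is that nothing in the plan says class predicts illness. Section 3.2.2 names it only as a possible modifier of the vaccine effect, which is a different matter from a difference in illness rate, and a main-effect term does not address effect modification. That is correct. If r = 1 the gain is nil, so the range must start at zero and be read as conditional.

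Four stronger readings are tempting, and the documents do not support them.

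- *The primary estimate is biased, or imbalance invalidates it.* Randomization keeps the unadjusted test valid, and its SE already allows for chance imbalance in class.
- *The trial falls short of 80% power.* If 0.4 is an overall value, as the two-class pilot suggests, the plan has its 80% and adjustment adds to it. A shortfall appears only under the within-class reading in step 5.
- *The gain reaches 5 points.* Putting the smaller k into the step 1 formula with one mean rate gives 0.6, 1.9 and 4.9 points at r = 1.25, 1.5 and 2. Allowing each class its own rate lowers these to 0.5, 1.5 and 4.1.
- *The omission inflates k in the re-estimation.* The overall k is the right planning value for an unadjusted model, and the sample size can only rise above 430. At the planned values a smaller within-class k would change nothing.

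The SAP promised in Section 14 may name covariates. That affects where the sentence should go, but it does not alter the model that Section 14 now states.

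**Conclusion.** The point holds as a matter of efficiency. The primary model as written uses none of three baseline factors known before allocation: class, which the design does not protect, and cohort and sex, which it does. For class the unrealised gain is 0 to about 4 points above the planned 80%, and about 0.5 to 1.5 points for class rate ratios of 1.25 to 1.5. A typical chance imbalance moves the log rate ratio by no more than about 0.03. These sizes rest on an overall k of 0.4, an even class mix and an assumed class rate ratio of 1.0 to 2.0. Validity of the planned test is not in question. The case for the change is that it costs little and must be pre-specified to be credible.

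**What to change.** In Section 14 or the SAP, before unblinding, pre-specify class (VP/1st semester versus 5th semester), cohort and sex as fixed covariates in the negative binomial model for the primary endpoint and secondary Endpoints 1-5. Make the adjusted rate ratio primary and report the unadjusted ratio as supportive. With a log link and no interaction, both estimate the same rate ratio, so the hypothesis in Section 14 stands. Endpoints 6 and 7 are left out because Section 12 has those data aggregated by arm before they reach the analyst.

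Leave the Section 8 blinded re-estimation on the overall k, which is conservative for an adjusted analysis.

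The cost is one sentence and a few parameters; no new data are needed. At fewer than 100 participants per semester, 430 participants need at least five intakes (430/100 = 4.3). That means at least four cohort terms, plus one each for class and sex. If none of these factors predicts illness, there is no gain.

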3.2.2 SECONDARY

OBJECTIVES	ENDPOINTS	JUSTIFICATION FOR ENDPOINTS
Secondary		

OBJECTIVES	ENDPOINTS	JUSTIFICATION FOR ENDPOINTS

 • To compare, between the same two groups over the same time period, 
 1) The rate of self-reported new episodes of respiratory illness (URI or ILI), DIA and UFI. 2) The rate of self-reported new episodes of 
 a) ILI b) URI c) DIA d) UFI 3) The rate of clinically-confirmed episodes of the study syndromes 4) The rate of laboratory-confirmed episodes of the study syndromes • First event, per protocol analysis (receipt of all 3 doses) and extended per protocol analysis (receipt of at least one dose) of primary endpoint and secondary endpoints 1-7 (primary analyses will focus on all events and intention-to-treat analyses). • Sub-group analyses for potential effect measure modification of Primary Endpoint and Secondary Endpoints 1-7 by 
 1) Sex (males or females) 2) Season (spring = January cohorts; summer = May cohorts; winter = September cohorts) 	
 1. Number of self-reported new episodes of respiratory illness (URI or ILI), DIA and UFI. 2. Number of self-reported new episodes of URI 3. Number of self-reported new episodes of ILI 4. Number of self-reported new episode of DIA 5. Number of self-reported new episodes of UFI 6. Number of clinically-confirmed episodes of the study syndromes, defined as an episode resulting in a visit to the RUSVM Student Health Services with a recorded ICD10 of J00 (acute nasopharyngitis); J11 (influenza due to unidentified influenza virus); R19.7 (diarrhea) or R50.9 (fever, unspecified). 7. Number of laboratory-confirmed episodes of the study syndromes, defined as clinically-confirmed episodes with laboratory diagnosis of influenza virus, respiratory syncytial virus or metapneumovirus (URI/ILI episodes) or rotavirus or norovirus (DIA episodes) . 	
For Secondary Endpoint 1, in any week a single participant could report one of the following:
 
 • No CID episode • One CID episode (URI or ILI or DIA or UFI) • Two CID episodes (either URI or ILI, and DIA) 
By this definition, a participant cannot experience more than two CID episodes within a week, as occurrence of URI together with ILI is considered an episode of ILI only, and occurrence of URI, ILI and/or DIA precludes the occurrence of UFI.
 
We also will attempt to determine impact on etiologically confirmed outcomes but we expect few episodes to meet this criteria and thus study power will be low. Etiological confirmation will be done for a limited range of pathogens only (influenza virus, respiratory syncytial virus, metapneumovirus, rotavirus and norovirus) through an independent research protocol (RUSVM IRB protocol #17-11-FL) and the test results sent back to the RUSVM Student Health Services.

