3.2.3 TERTIARY

OBJECTIVES	ENDPOINTS	JUSTIFICATION FOR ENDPOINTS
Tertiary/Exploratory		

 Among the vaccinated group only, to compare Primary Endpoint and Secondary Endpoints 1-7 between high responders and low responders, defined by RVNA titers measured by rapid fluorescent foci inhibition test (RFFIT) at day 180 after first vaccination. Explore latency period and duration of effect on Primary Endpoint and Secondary Endpoints 1-5. Explore the effect of dose (1 vs. 2 vs. 3) on Primary 	
 Primary Endpoint and Secondary Endpoints 1-7 Primary Endpoint and Secondary Endpoints 1-5 Primary Endpoint and Secondary Endpoints 1-5 	See above

OBJECTIVES	ENDPOINTS	JUSTIFICATION FOR ENDPOINTS
Endpoint and Secondary Endpoints 1-5.		

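### Section 14 gives the seven secondary endpoints the same unadjusted 0.05 significance rule as the primary, with no testing order and no supportive label

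*Combined protocol and SAP*

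**What the plan says.** Section 14 introduces the negative binomial model for the "comparison of incidence rates of CID episodes (primary endpoint and secondary endpoints 1-7) between the treatment arms". It then states one null and one alternative hypothesis and the rule that "Statistical significance will be controlled at the 2-sided, 0.05 alpha level, and the estimated rate ratio compared with 1". It adds that "Statistical significance at the pre-specified alpha level will be based on a Wald testing procedure". The reporting sentence that follows again takes the primary and the seven secondary endpoints together and promises rates, rate ratios and 95% confidence intervals. The section ends by deferring detailed methods for the primary and secondary endpoints to a SAP.

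Section 3.2 ranks the endpoints as primary, secondary and tertiary. Section 3.2.2 lists seven secondary endpoints and then asks for first-event, per-protocol and extended per-protocol versions of all eight. It also asks for "Sub-group analyses for potential effect measure modification of Primary Endpoint and Secondary Endpoints 1-7 by" sex, season and class, and for "Subset analyses of Primary Endpoint and Secondary Endpoints 1-7 in the subset of participants" who are not immunosuppressed. The label "Tertiary/Exploratory" appears in Section 3.2.3 only. Section 8 sizes the trial on the primary objective alone, with "Alpha level = 0.05".

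**The concern.** Section 14 speaks of significance as controlled at 0.05. That is true of each test taken singly, but not of eight tests taken together. With no order, no alpha allocation and no supportive label, the plan leaves room for a trial with a null primary and one secondary p < 0.05 to report that secondary result as statistically significant at the pre-specified level.

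The risk is practical here. Section 3.2.1 says that the biological basis of any non-specific effect is unknown and that there is at present no biological reason to separate the syndromes. There is therefore no prior expectation about which syndrome should respond, and an isolated positive on any one of them could be offered as evidence of a non-specific effect. Section 2.1 says that recognition of such an effect could bear on public health decisions.

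**Working it through.** **1. The plan's own figure.** Inputs from Section 8: control rate r0 = 2 per 26 weeks, rate ratio 0.75 (so r1 = 1.5), mean participation t = 0.8 of the period, dispersion k = 0.4, two-sided alpha 0.05, power 0.8.

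- V = (1/t)(1/r0 + 1/r1) + 2k = 1.25 × (0.5 + 0.6667) + 0.8 = 2.258
- n per arm = (1.960 + 0.842)² × V / (ln 0.75)² = 7.849 × 2.258 / 0.0828 = 214.2, rounded up to 215
- Total 430, as stated. Power at 215 per arm is 0.802.

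The calculation spends the whole 0.05 on one test, the primary.

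**2. Seven secondary tests at 0.05, no vaccine effect.**

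- Independent tests: 1 − 0.95⁷ = 0.302
- Upper bound (Bonferroni): 7 × 0.05 = 0.35
- Perfectly correlated tests: 0.05

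**3. Allowing for correlation.** The endpoints overlap. Endpoint 1 combines the syndromes counted separately in Endpoints 2-5, and the laboratory-confirmed episodes are a subset of the clinically confirmed ones. The documents give no correlations, so a range is shown for equally correlated normal test statistics (400,000 draws):

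| Assumed common correlation | Chance of at least one p < 0.05 among seven |
|---|---|
| 0 | 0.301 |
| 0.3 | 0.270 |
| 0.5 | 0.229 |
| 0.7 | 0.178 |
| 0.8 | 0.149 |
| 0.9 | 0.114 |

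**4. Simulating the overlap directly.** From Section 8: 215 per arm, 2 × 0.8 = 1.6 expected episodes per person, k = 0.4. Negative binomial Wald tests were run on 3,000 null trials per scenario. The syndrome shares, the proportions of episodes confirmed in clinic and of those confirmed in the laboratory, and whether syndromes share one frailty are all assumptions.

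| URI/ILI/DIA/UFI share (%) | Frailty | Clinic / lab (%) | Any of seven p < 0.05 | Same, and primary not significant |
|---|---|---|---|---|
| 55/15/20/10 | shared | 15 / 20 | 25.1% | 20.6% |
| 55/15/20/10 | separate | 15 / 20 | 27.8% | 22.6% |
| 75/10/10/5 | shared | 10 / 10 | 22.8% | 17.6% |
| 25/25/25/25 | shared | 30 / 30 | 24.0% | 19.3% |
| 30/30/30/10 | separate | 10 / 40 | 25.5% | 20.1% |
| 90/5/3/2 | shared | 3 / 5 | 19.1% | 14.1% |
| 85/5/8/2 | shared | 50 / 5 | 20.7% | 15.8% |

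Simulation error is about √(0.25 × 0.75 / 3,000) = 0.8 percentage points. The last two rows are lower partly because sparse endpoints seldom reach p < 0.05 with a Wald test. The primary test rejected in 4.6% to 5.6% of trials across the seven scenarios, so its own error rate is intact.

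A separate simulation of 40,000 trials, with assumed mean counts of 0.8 (URI), 0.3 (ILI), 0.35 (DIA) and 0.15 (UFI), 10% of episodes clinic-confirmed and 20% of those laboratory-confirmed, gave 0.247.

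**5. After the fix.** If the seven secondaries are tested only after a significant primary, the first Holm step is 0.05/7 = 0.00714. Seven independent tests at that level give 1 − (1 − 0.00714)⁷ = 0.049. The primary stays at 0.05, so the total stays at 430.

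**The case against.** The best defence is that the plan does have a hierarchy of endpoints: one primary hypothesis (Section 3.1), one primary endpoint, a sample size resting on it, and a stated emphasis on all-events, intention-to-treat analysis. This stands. A reader might infer from the shared rule that the primary conclusion itself is compromised; it is not. But tiering endpoints is not a testing procedure, and Section 14 applies the same rule across the first two tiers.

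Second, the 0.05 sentence refers to a single rate ratio and a single hypothesis, after a sentence that models CID episodes, so it could be read as covering the primary alone. That reading is possible but strained, because the model is introduced for all eight endpoints and the reporting sentence names all eight again. If it is what the sponsor intends, one sentence would settle it.

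Third, methods are deferred to a SAP. That makes the SAP a proper place for the fix. It does not show that the SAP contains a rule, and the supplied documents have no SAP text on multiplicity.

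Fourth, no text says that an isolated secondary p < 0.05 will be called significant. This is correct: the plan permits the claim and does not announce it.

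**Conclusion.** The gap is real and limited to claims on secondary endpoints. With no vaccine effect, the chance of at least one p < 0.05 among Secondary Endpoints 1-7 is 30% under independence and roughly 19-28% in the simulations, and 14-23% of simulated null trials had a significant secondary beside a non-significant primary. At an assumed common correlation of 0.9 the first figure falls to 11%, still more than twice 0.05. The documents give no syndrome shares, correlations or confirmation proportions, so a flat statement of one in four would claim more than they support.

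A reader might also count everything in Section 3.2.2: eight endpoints in five analyses (40 treatment comparisons) and eight endpoints by three modifiers (24 subgroup analyses), each as a fresh chance of a false positive. The documents do not support that as a measure of error. Allocation happens when the participant attends for the first injection (Section 11.2), so the at-least-one-dose analysis should nearly duplicate intention-to-treat. The first-event, per-protocol and subset analyses rework the same data. For effect modification, no interaction test and no 0.05 rule is stated, so no error rate can be assigned. What is missing for these analyses is a statement of their inferential status.

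**What to change.** In Section 14 or the SAP, before outcomes are compared by arm:

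- Limit the 0.05 significance statement to the intention-to-treat, all-events comparison of composite CID.
- State that Secondary Endpoints 1-7 and the first-event, per-protocol, extended per-protocol, subset and subgroup analyses are supportive. Report them as estimates with 95% confidence intervals, described as unadjusted, and make no significance claim.
- If a confirmatory secondary claim is wanted, test Endpoints 1-7 only after a significant primary, by a stated fixed sequence or Holm at 0.05. In a fixed sequence, the laboratory-confirmed endpoint, for which Section 3.2.2 expects low power, would probably block anything placed after it.

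The cost is a few sentences. Sample size, data collection and the primary test do not change. The downside is that an isolated secondary p < 0.05 can no longer be called statistically significant.

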12 DATA COLLECTION METHODS

After enrollment, participants will complete a questionnaire that will capture data on relevant baseline characteristics including sex, age, health and vaccination status. (Baseline CRF; Appendix C). Participants will complete a short survey each week, starting in study week 3, to capture self-reported episodes of illness (respiratory, diarrheal and febrile illness; Primary Endpoint and Secondary Endpoints 1-5) in the preceding week (Appendix G). Surveys will be sent by email to all participants each Monday. Participants who have not completed the survey by Wednesday afternoon will be sent a request by email to complete the survey for the preceding week. Surveys will be sent weekly, for 26 weeks. A participant is considered to have completed the study one week after receipt of the final (26th) weekly survey for that participant's cohort.

As an incentive to enhance participant retention and response rates in weekly illness surveys, all participants who complete a weekly survey will be entered into a draw each week for a chance to win a EC\$25 gift voucher to a food/beverage vendor on the RUSVM campus. Selection of a winner each week will be done by computer-generated random sampling. The weekly winner will be notified by email in the week following the draw.

Clinically- and laboratory-confirmed episodes of study syndromes (Secondary Endpoints 6 & 7) will be collected by study personnel at RUSVM Student Health Services, as part of the

routine clinic visits and diagnostics. At the end of each 26-week observation period for each study cohort, data from that cohort will be compiled by the director of the RUSVM Student Health Services, anonymized to protect privacy and aggregated by study arm, before being sent to the Data Analyst who will conduct the analysis.

Occurrence of expected Adverse Events (Safety Endpoint 1) will be solicited in an online survey (Appendix H) sent to participants 3 days after receiving an injection (for dose 1, 2 and 3). Occurrence of unsolicited adverse events and serious adverse events (Safety Endpoint 2) will be captured by study personnel at RUSVM Student Health Services through completion of an Adverse Event form (Appendix I; See **Section 15.3, Identification of Adverse Events** for details).

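### The Wald test and interval prescribed for laboratory-confirmed episodes (secondary Endpoint 7) break down if one arm has no events, and no fallback is stated

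*Combined protocol and SAP*

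**What the plan says.** Section 14 sets one method for all these endpoints. The scope it gives is "The comparison of incidence rates of CID episodes (primary endpoint and secondary endpoints 1-7) between the treatment arms". As to the model, it says that this analysis "will be performed using a negative binomial regression model, which accounts for different lengths of observation period". Each participant's episode count is modelled on treatment group, with weeks of observation as the offset. On testing it says: "Statistical significance at the pre-specified alpha level will be based on a Wald testing procedure". Rates and the rate ratio are to be reported with 95% intervals for every one of these endpoints.

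Section 3.2.2 defines Endpoint 7 narrowly. It requires a visit to Student Health Services with one of four listed ICD10 codes, plus a laboratory diagnosis of one of five viruses. Of these etiologically confirmed outcomes the plan says: "we expect few episodes to meet this criteria and thus study power will be low". The same section plans analyses of Endpoint 7 by sex, season (three levels) and class, and also per protocol.

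Section 12 says that the Endpoint 6 and 7 data from each cohort are "anonymized to protect privacy and aggregated by study arm, before being sent to the Data Analyst who will conduct the analysis".

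The supplied text states no minimum event count and no exact, score or descriptive-only alternative. Section 14 refers further detail to a SAP, and no SAP text is among the supplied pages.

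**The concern.** The plan concedes low power for Endpoint 7. The problem here is a separate one. A low-powered analysis still returns an estimate and an honest, wide interval. With an empty arm, the prescribed analysis returns neither. The likelihood keeps rising as the log rate ratio moves towards minus (or plus) infinity, and its standard error grows much faster than the estimate does. The Wald statistic therefore goes to zero and the interval covers everything. Software may still print a p-value near 0.99, which a reader could take for a result.

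The statistic also stops responding to the data: 10:0 looks no more convincing than 6:0. What is at stake is whether the rate ratio, interval and p-value promised for Endpoint 7, and for its subgroups, would exist and mean anything.

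**Working it through.** **1. The plan's own figure.** The inputs in Section 8 are a control rate of 2 per 26 weeks, rate ratio 0.75 (so 1.5 on vaccine), participation 0.8 of the period, dispersion 0.4, two-sided alpha 0.05 and power 0.8.

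- V = (1/0.8) × (1/2 + 1/1.5) + 2 × 0.4 = 2.258
- n per arm = (1.960 + 0.842)² × 2.258 / (ln 0.75)² = 214.2, rounded up to 215, or 430 in total. This matches Section 8.
- Expected self-reported episodes are 215 × 2 × 0.8 = 344 on control and 344 × 0.75 = 258 on vaccine. An empty arm is not a risk for the primary endpoint.

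**2. What the prescribed method returns.** The model was fitted with 215 per arm and equal follow-up of 20.8 weeks (0.8 × 26). The comparator is the exact conditional test with equal person-time. For n events against 0, two-sided p = 2 × 0.5ⁿ, and the upper 95% limit for the rate ratio is (1 − 0.025^(1/n)) / 0.025^(1/n). For n = 6, p = 2 × 0.5⁶ = 0.031. Since 0.025^(1/6) = 0.541, the limit is 0.459/0.541 = 0.85.

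| Placebo:vaccine events | Prescribed Wald p | Prescribed RR interval | Exact p | Exact RR interval |
|---|---|---|---|---|
| 5:0 | above 0.99 (k fixed at 0.4) | 0 to infinity | 0.0625 | 0 to 1.09 |
| 6:0 | 0.995 (k estimated), 0.999 (k = 0.4) | 0 to infinity | 0.031 | 0 to 0.85 |
| 10:0 | 0.995 (k estimated), 0.999 (k = 0.4) | 0 to infinity | 0.0020 | 0 to 0.45 |

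A second maximum-likelihood program gave no standard errors for any empty-arm split.

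With both arms non-empty the picture is milder. At 8:3 the fit gave an interval of 0.10 to 1.41, against an exact 0.06 to 1.56. The dispersion was not identifiable (the iteration limit was reached) and the second program again gave no standard error, but the interval is usable, if somewhat narrow.

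**3. How often this could happen.** The documents give no count for Endpoint 7, so the expected control-arm count m is an assumption. Taking Poisson counts and a rate ratio of 0.75:

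- P(at least one empty arm) = 1 − (1 − e^(−m))(1 − e^(−0.75m))
- P(significance call changes) = P(one arm empty and the other has at least 6 events) = e^(−m) × P(Poisson(0.75m) ≥ 6) + e^(−0.75m) × P(Poisson(m) ≥ 6). Six is the smallest n with exact p below 0.05.
- For m = 2 the second formula gives 0.1353 × 0.0045 + 0.2231 × 0.0166 = 0.0043.

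| Assumed control events m | Any empty arm | Significance call changes |
|---|---|---|
| 2 | 33% | 0.4% |
| 3 | 15% | 1.0% |
| 4 | 7% | 1.2% |
| 5 | 3% | 1.0% |
| 8 | 0.3% | 0.2% |

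At m = 2, the 33% includes e^(−3.5), about 3%, in which both arms are empty.

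**4. Subgroups.** Suppose 10 control events, rate ratio 0.75, spread evenly over the three seasons. Overall, an empty arm has a chance below 0.1%. Within one season (m = 3.33) it is about 11%, and in at least one of three about 1 − (1 − 0.115)³ = 31%.

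**5. Form of the data.** Arm totals carry no participant-level counts or offsets. They cannot support the model in Section 14 or estimate dispersion, whatever the event count. They do support a conditional comparison, which needs only two counts and two person-time totals.

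**The case against.** The strongest reply concerns size. In most empty-arm outcomes at the lower assumed counts the exact test is non-significant too (5:0 gives 0.0625), so few conclusions would be rescued. That stands: the change in the significance call is at most about 1.2% over the counts tried. A reader who sets the 33% beside the 6:0 example might infer that clear effects would often be missed. The two seldom occur together, and the figures do not support that inference.

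A reader might also infer that Endpoint 7 will have only two to four events. Section 3.2.2 says few and gives no number. At 8 expected control events the overall risk is 0.3%.

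Nor is the method broken for all sparse data. The 8:3 fit shows that the clear breakdown is the empty arm.

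Finally, a fallback may be written in the SAP that Section 14 promises. That cannot be excluded. But Section 14 does not leave the choice open: it names the Wald procedure for these endpoints, and that rule is what fails. Low power, a secondary endpoint and an intact primary analysis limit the importance of the point without removing it.

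**Conclusion.** The point holds as a minor one. The failure with an empty arm is mathematical and does not depend on software. How often it would arise is unknown, because the documents give no expected count. The percentages rest on assumed counts, Poisson variation, a rate ratio of 0.75 and equal person-time. On those assumptions an empty arm matters at roughly five or fewer expected control events overall, and at higher totals once events are divided by season, sex or class. What a repair buys is mainly a valid, finite upper limit for the rate ratio, and only rarely a different significance call.

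The documents do not support extending the point to Endpoint 6. The expectation of few episodes refers to etiologically confirmed outcomes, not to clinic-recorded ones.

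**What to change.** In Section 14 or the SAP, state that Endpoint 7 and its subgroup analyses will use an exact conditional (binomial) comparison of arm event counts given person-weeks, with an exact or mid-p 95% interval for the rate ratio. If both arms are empty, report counts only. Under the null, the vaccine share of events is T_v/(T_v + T_c), where T is person-weeks. The interval for the binomial share π converts to a rate ratio as π/(1 − π) × T_c/T_v.

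This costs one sentence and fits the arm-level data flow in Section 12. Totals compiled by cohort already give season; sex and class need the totals split the same way.

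There are two drawbacks. The test ignores extra-Poisson variation, which is anti-conservative in principle. If k = 0.4 applied, 10 events in 215 people would inflate the variance by 0.4 × 10/215, about 2%, which is negligible. The exact version is also slightly conservative because the counts are discrete.

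Do not extend the rule to Endpoint 6 unless a numeric event threshold is fixed in advance. Otherwise the choice of test would be made after seeing the data.
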